to the corresponding endpoint for evaluation. For patients who receive rescue therapy starting at Week 16, the last nonmissing observation at or before rescue will be carried forward to subsequent time points for evaluation.

5. Modified last observation carried forward (mLOCF): For all continuous measures including safety analyses, the mLOCF will be a general approach to impute missing data unless otherwise specified. For patients who receive rescue therapy starting at Week 16, the last nonmissing observation at or before rescue will be carried forward to subsequent time points for evaluation. For all other patients discontinuing from the study or the study treatment for any reason, the last nonmissing postbaseline observation before discontinuation will be carried forward to subsequent time points for evaluation. After mLOCF imputation, data from patients with nonmissing baseline and postbaseline observations will be included in the analyses. The mLOCF will be used as a sensitivity method to the mBOCF method with respect to the secondary endpoints.
6. Other methods for data imputation for analysis of endpoints other than mTSS may be used and will be described in the SAP.

Any change to the data analysis methods described in the protocol will require an amendment ONLY if it changes a principal feature of the protocol. Any other change to the data analysis methods described in the protocol, and the justification for making the change, will be described in the SAP and the clinical study report (CSR). Additional exploratory analyses of the data will be conducted as deemed appropriate.

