12.2.7. Efficacy Analyses

Secondary analyses:

1. Comparison between baricitinib and placebo in change from baseline to Week 12 in HAQ-DI score: An ANCOVA model with treatment, country, joint erosion status, and baseline score in the model will be used to test the treatment difference between baricitinib and placebo in change from baseline to Week 12 in HAQ-DI. The mBOCF and mLOCF approaches as described above will be used to impute missing data.
2. Comparison between baricitinib and placebo in change from baseline to Week 12 in DAS28-hsCRP: An ANCOVA model with treatment, country, joint erosion status, and baseline score in the model will be used to test the treatment difference between baricitinib and placebo in change from baseline to Week 12 in DAS28-hsCRP. The mBOCF and mLOCF approaches as described above will be used to impute missing data.
3. Comparison between baricitinib and placebo in proportion of patients achieving an SDAI score ≤ 3.3 at Week 12: A logistic regression model with treatment, country, and joint erosion status in the model will be used to test the treatment difference between baricitinib and placebo in the proportion of patients achieving an SDAI score ≤ 3.3 response at Week 12. The NRI method as described above will be used to impute missing data.
4. Comparison between baricitinib and placebo in mean duration of morning joint stiffness in the 7 days prior to Week 12: An ANCOVA model with treatment, country, joint erosion status, and baseline score (Day 1 on the diaries) in the model will be used to test the treatment difference between baricitinib and placebo in mean duration of morning joint stiffness in the 7 days prior to Week 12. Refer to the SAP for more details.
5. Comparison between baricitinib and placebo in mean severity of morning joint stiffness in the 7 days prior to Week 12: An ANCOVA model with treatment, country, joint

erosion status, and baseline score (Day 1 on the diaries) in the model will be used to test the treatment difference between baricitinib and placebo in mean severity of morning joint stiffness in the 7 days prior to Week 12. Refer to the SAP for more details.

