5.2. Determination of Sample Size

Approximately 288 patients (144 in baricitinib, 144 in placebo) will provide:

- 99% power to detect a difference between the baricitinib and placebo treatment groups in ACR20 response rate (60% versus 35%) at Week 12 based on a 2-sided chi-square test at a significance level of 0.05.

The sample size and power estimates were obtained using nQuery® Advisor 7.0.

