6.1. General Considerations

This plan describes *a priori* statistical analyses for efficacy, health outcomes, and safety that will be performed.

Statistical analysis of this study will be the responsibility of Lilly.

For continuous measures, summary statistics will include the sample size, means, standard deviations (SDs), medians, minimums, 1st quartiles (Q1), 3rd quartiles (Q3), and maximums.

For categorical measures, summary statistics will include the sample size, frequency counts, and percentages.

All statistical tests of treatment effects will be performed at 2-sided significance levels of 0.05, unless otherwise stated.

All p-values will be rounded up to 3 decimal places. For example, any p-value strictly greater than 0.049 and less than or equal to 0.05 will be displayed as 0.050. This guarantees that on any printed statistical output, the unrounded p-value will always be less than or equal to the displayed p-value. A displayed p-value of 0.001 will always be understood to mean ≤ 0.001 . Likewise, any p-value displayed as 1.000 will be understood to mean > 0.999 and ≤ 1 .

Lilly will use both an effectiveness estimand (that is, the relative effect attributable to the originally randomized treatments, baricitinib and placebo, at the primary time point in all treated patients, even if patients change treatment) and an efficacy estimand (that is, the relative effect attributable to the originally randomized treatments, baricitinib and placebo, at the primary time point in all treated patients if taken as directed) to evaluate efficacy measures at the primary time point of Week 12 for Study JAGS. All primary and secondary endpoints related to improvements in symptomatic features (that is, RA signs and symptoms, physical function, and patient-reported outcomes) are assessed prior to patients having the option to receive rescue therapy. Therefore, the only practical difference between the efficacy and effectiveness estimands for these endpoints concerns assumptions about patient response after permanent discontinuation of study drug or from the study prior to the analysis time point.

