6.13. Health Outcomes Analyses

6.13.1. Diary Data

6.13.1.1. Data Handling and Missing Data Imputation

The paper diary data (duration of morning joint stiffness, severity of morning joint stiffness, worst joint pain, worst tiredness, and recurrence of morning joint stiffness during the day) will be assessed daily from Week 0 (Visit 2) to Week 12 (Visit 7). The primary analysis is based on the scores collected in the 7 days prior to the Week 12 visit date. Similar analysis will be done for 7 days prior to each scheduled visit (Week 1, Week 2, Week 4, and Week 8) using the primary analysis method. The supportive analysis is based on daily data modeled by weekly means. The weeks are defined as follows: Day 1 on diary, Days 2-8 (Week 1), Days 9-15 (Week 2), and so on up to Days 79-85 (Week 12).

For the primary analysis, the average of the scores collected in the 7 days prior to Week 12 will be used. If there are fewer than 4 nonmissing scores, the 7-day window will be shifted back in time (toward baseline) 1 day at a time until there are 4 nonmissing scores available in the 7-day window. Then the average of the 4 scores will be used in the Week 12 analysis. This will be repeated for each scheduled visit (week 1, week 2, week 4, week 8) prior to week 12.

For patients who discontinue the study or permanently discontinue the study treatment, the scores collected in the last 7 days prior to discontinuation will be used in the analysis. If a patient undergoes a temporary interruption of study drug at the time of study database lock, this patient will be treated as having permanently discontinued from study drug in the missing data imputation. If there are fewer than 4 nonmissing scores, a similar approach will be used to find 4 nonmissing scores in a 7-day window and the average score will be used in the Week 12 analysis. Patients who do not have at least 4 scores in any postbaseline 7-day window up to Week 12 will have their Day 1 score carried forward to the endpoint for analysis. If the Day 1 value cannot be obtained, the first available postbaseline score will be used to impute the Day 1 score so that the patient can be included in the analysis.

For the analysis at each scheduled visit using the primary analysis method, the same imputation rule for the primary analysis will be used. The imputed value for missing Day 1 measures from postbaseline assessments as described in the primary analysis will not be used in the change from Day 1 analysis.

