6.13.1.2. Analysis of Diary Data

The effect of baricitinib compared to placebo up to Week 12 with regard to patient-reported outcomes (PROs) will be evaluated by the following measures:

- Duration of morning joint stiffness**

Duration of morning joint stiffness is a patient-administered item that allows for the patients to enter the length of time in minutes that their morning joint stiffness lasted each day (using a paper diary) through Visit 7 (Week 12). Duration of morning stiffness will be recorded in minutes. Durations recorded as longer than 12 hours (720 minutes) will be truncated to 720 minutes for analysis.

A nonparametric method involving the Hodges-Lehmann estimator will be used to test the treatment difference in the average durations (of morning joint stiffness) collected in the 7 days prior to Week 12. For the comparison between the baricitinib group and the placebo group, the median score and its 95% CI from the Hodges-Lehmann estimator will be presented. The p-value for the median difference will be calculated using the Wilcoxon rank-sum test. A 95% CI for the median score within each treatment group will be calculated using distribution-free confidence limits. Missing data will be handled as described for the main analysis in Section 6.13.1.1. This analysis of duration of morning joint stiffness will be

conducted using the mITT population. The PP population results will be used as supportive evidence to the mITT results. The primary analysis of duration of morning joint stiffness will also be repeated for each scheduled visit using the mITT population.

In addition, the average change of duration (of morning joint stiffness) from Day 1 across the 7 days prior to Week 12 on diary will be compared between the baricitinib group and the placebo group using the same analysis method described. The imputed value for missing Day 1 durations from postbaseline assessments as described in Section 6.13.1.1 will not be used in the change from Day 1 analysis.

- **Severity of morning joint stiffness NRS**

Severity of morning joint stiffness NRS is a patient-administered, single-item, 11-point horizontal scale anchored at 0 and 10, with 0 representing “no joint stiffness” and 10 representing “joint stiffness as bad as you can imagine.” Patients rate their morning joint stiffness each day (using a paper diary) up to Visit 7 (Week 12) by selecting 1 number that describes their overall level of joint stiffness at the time they wake up.

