An ANCOVA model will be used to test for treatment differences in the severity of morning joint stiffness NRS collected in the 7 days prior to Week 12, with treatment, country/region, and baseline joint erosion status (1-2 joint erosions plus seropositivity versus at least 3 joint erosions) as fixed effects and Day 1 value as a covariate. Missing data will be handled as described for the primary analysis in Section 6.13.1.1. Type III sums of squares for the LS means will be used for the statistical comparison; the 95% CI will also be reported. The LS mean difference, SE, CI, and p-value will be presented for the treatment difference between the baricitinib group and the placebo group. This analysis of severity of morning joint stiffness NRS will be conducted using the mITT population. The PP population results will be used as supportive evidence to the mITT results. The primary analysis of severity of morning joint stiffness NRS will also be repeated for each scheduled visit using the mITT population.

- **Tiredness severity NRS (“Worst Tiredness”)**

Worst tiredness NRS is a patient-administered, single-item, 11-point horizontal scale anchored at 0 and 10, with 0 representing “no tiredness” and 10 representing “as bad as you can imagine.” Patients rate their tiredness each day (using a paper diary) through Visit 7 (Week 12) by selecting the 1 number that describes their worst level of tiredness during the past 24 hours.

The primary analysis of “Worst tiredness” will be analyzed in a similar manner as described for severity of morning joint stiffness NRS. This primary analysis of “Worst tiredness” will be conducted using the mITT population. The PP population results will be used as supportive evidence to the mITT results. The primary analysis of “Worst tiredness” will also be repeated for each scheduled visit using the mITT population.

- **Pain severity NRS (“Worst Joint Pain”)**

Worst Joint Pain NRS is a patient-administered, single-item, 11-point horizontal scale anchored at 0 and 10, with 0 representing “no pain” and 10 representing “pain as bad as you can imagine.” Patients rate their joint pain each day (using a paper diary) through Visit 7

(Week 12) by selecting the 1 number that describes their worst level of joint pain during the past 24 hours.

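### Duration of morning joint stiffness: the SAP's main test is an unadjusted Wilcoxon test, replacing without explanation the protocol's analysis adjusted for Day 1 and both randomisation factors

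*SAP*

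**What the plan says.** Protocol 12.2.7, secondary analysis 4, specifies for this endpoint: "An ANCOVA model with treatment, country, joint erosion status, and baseline score (Day 1 on the diaries) in the model will be used". It refers to the SAP for details. Protocol 12.2.1 allows changes of method that are not principal features without an amendment, but says that each change "and the justification for making the change, will be described in the SAP" and the clinical study report.

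SAP 6.11.2 lists the endpoint as secondary and points to 6.13. SAP 6.13.1.2 then caps durations at 720 minutes, estimates the treatment difference by Hodges-Lehmann, and states: "The p-value for the median difference will be calculated using the Wilcoxon rank-sum test". The test has no Day 1 term, no country or region term and no erosion term. A further comparison of change from Day 1 uses the same unadjusted method. No reason for leaving ANCOVA is given.

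In the same section, severity of morning stiffness is analysed by ANCOVA with treatment, country/region and erosion status "as fixed effects and Day 1 value as a covariate". Worst tiredness and worst joint pain follow that model.

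**The concern.** The SAP made two changes at once. It moved from minutes to ranks, and it dropped the baseline value and both stratification factors. The first is reasonable for a skewed duration. The second does not follow from it, because a rank-based ANCOVA keeps the ranks and still adjusts.

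The change also departs from the SAP's own general rules: 6.1 plans baseline- and stratum-adjusted ANCOVA for continuous health outcomes, and 6.2 adjusts efficacy and health outcomes models for the stratifying variables.

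At stake is precision on one secondary endpoint. Day 1 is already collected, the strata are already used in randomisation, and a chance Day 1 imbalance would go straight into the main test. False-positive risk and the ACR20 conclusion are not at stake.

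**Working it through.** **Inputs from the documents.** Sample size: "Approximately 288 patients (144 in baricitinib, 144 in placebo) will provide" the stated power (SAP 5.2). Significance level 0.05, two-sided (SAP 6.1). Cap of 720 minutes (SAP 6.13.1.2). Stratification by country and joint erosion status (SAP 5.3).

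**Not in the documents, so assumed.** SD, effect size and Day 1 to Week 12 correlation for duration; regional and erosion shares.

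**1. The plan's own power figure.** It concerns ACR20 only: "99% power to detect a difference between the baricitinib and placebo treatment groups in ACR20 response rate (60% versus 35%) at Week 12". With pooled variance and p̄ = 0.475:

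Φ{[0.25·√144 − 1.960·√(2·0.475·0.525)] / √(0.60·0.40 + 0.35·0.65)} = Φ{(3.000 − 1.384)/0.684} = Φ(2.36) = 0.991.

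The 99% reproduces. No power is stated for duration.

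**2. Variance removed by adjusting for Day 1.** If r is the rank correlation of Day 1 with Week 12, the adjusted rank comparison has about 1 − r² of the unadjusted variance. For an underlying normal correlation ρ on the log scale, r = (6/π)·asin(ρ/2).

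| ρ | 1 − r² | Sample-size factor 1/(1 − r²) |
|---|---|---|
| 0.2 | 0.963 | 1.04 |
| 0.3 | 0.917 | 1.09 |
| 0.5 | 0.767 | 1.30 |
| 0.7 | 0.534 | 1.87 |

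Power of the adjusted test when the unadjusted one has 80% is Φ{(1.960 + 0.842)/√(1 − r²) − 1.960}. This gives 83.6%, 89.9% and 97.5% at r = 0.3, 0.5 and 0.7.

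**3. Simulation.** 144 per arm; lognormal durations with median 60 minutes, capped at 720; region split 80/20; erosion split 30/70; stratum effects 0.2 SD; 4000 replicates per cell (5000 under the null). Power (%) for an effect of 0.30 log-SD, shown as log-SD 1.0 / log-SD 1.3:

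| ρ | Wilcoxon, Week 12 (planned) | Wilcoxon, change from Day 1 | Raw-scale ANCOVA (protocol) | Rank ANCOVA |
|---|---|---|---|---|
| 0 | 68.9 / 67.8 | 35.7 / 34.0 | 55.6 / 52.0 | 69.4 / 67.7 |
| 0.2 | 69.4 / 69.0 | 40.7 / 40.5 | 55.5 / 53.9 | 71.4 / 71.1 |
| 0.3 | 70.2 / 68.4 | 46.2 / 42.8 | 57.9 / 54.9 | 73.4 / 72.3 |
| 0.5 | 68.2 / 69.2 | 57.0 / 54.6 | 61.2 / 60.1 | 79.8 / 80.4 |
| 0.7 | 69.5 / 68.8 | 78.3 / 77.1 | 75.8 / 72.3 | 92.2 / 91.3 |

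Other effect sizes (log-SD 1.0), Wilcoxon against rank ANCOVA:

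| ρ | Effect 0.20 | Effect 0.36 |
|---|---|---|
| 0.2 | 35.9 v 37.5 | 83.7 v 85.0 |
| 0.3 | 36.3 v 38.5 | 84.4 v 87.6 |
| 0.5 | 38.6 v 48.8 | 83.8 v 91.8 |
| 0.7 | 38.1 v 61.9 | 84.1 v 97.9 |

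Across all cells the gain is about 0 points at ρ = 0, 1-2 at 0.2, 2-4 at 0.3, 8-12 at 0.5 and 14-24 at 0.7. The strata alone contribute about 0-1 point. Under the null, rejection was 4.8-5.4% for the Wilcoxon test and 4.8-5.1% for the rank ANCOVA.

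**4. Sensitivity to the assumptions.** A second simulation used stratified blocks, three countries, 5-minute rounding and an effect giving the Wilcoxon test 77-79% power. The rank ANCOVA had 78%, 82%, 87% and 96% at ρ = 0, 0.3, 0.5 and 0.7. The variance ratios were 0.98, 0.90, 0.76 and 0.53, close to step 2. Null rejection was 4.1-5.3% for the Wilcoxon test and 4.7-6.0% for the rank ANCOVA. The simulation SE is about 0.3 points; the larger null runs in step 3 do not repeat the 6.0%.

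**5. Does the change-from-Day-1 analysis make up the loss?** No. On a log scale with equal variances, a change has 2(1 − ρ) times the variance of the Week 12 value, so it breaks even only at ρ = 0.5. In raw minutes it does worse: it lies below the Week 12 Wilcoxon test at every ρ up to 0.5. At 0.7 it is above that test in step 3 (78.3 v 69.5) but below it in step 4 (74 v 79). It is below the rank ANCOVA in every cell of both simulations.

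**The case against.** The strongest reply is that this is a choice between valid methods. The Wilcoxon test controls type I error, comes with a matching estimate and interval in minutes, and beats the protocol's raw-scale ANCOVA by 7-16 points at correlations from 0 to 0.5 (it loses 4-6 at 0.7). Over most of the assumed range, then, the SAP improved on the protocol. The shortfall exists only against a method that neither document names. All of this is correct.

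The correlation is also unknown, and a single diary day set against a 7-day mean 12 weeks later may correlate only modestly. At 0.2-0.3 the gain is 1-4 points, and the documents do not support 0.7 in particular. That stands, and it limits the claim about size. It does not favour leaving Day 1 out, since adjustment cost nothing even at zero correlation.

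Duration is handled nonparametrically for the tablet version too (SAP 6.16.1.1), so the choice looks deliberate, and 0-10 ratings are a different kind of variable. That explains the ranks but not the missing covariates. The change-from-Day-1 analysis does bring Day 1 in, but as an additional comparison without the strata.

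Finally, the missing justification could be cured by one sentence. On its own it would be a documentation gap and would not require a new test. The case for changing the test rests on precision.

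**Conclusion.** The point holds. The main test for a named secondary endpoint leaves out a baseline already collected and both randomisation factors, contrary to the protocol and to the SAP's treatment of the other three secondary diary endpoints, and no reason is stated. Against a rank ANCOVA, the cost ranges from nothing at correlation 0 to 14-24 points of power at 0.7, or a sample-size factor of 1.04 to 1.87 for correlations of 0.2 to 0.7. These figures rest on assumed lognormal durations, effects of 0.20 to 0.36 log-SD and the correlations shown. The direction is firm; where in the range the trial falls cannot be known from the documents. The issue is efficiency and an unexplained departure, not validity. No sample-size statement changes.

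**What to change.** Before the single unblinding after final database lock:

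- Make the main test a rank-based ANCOVA of the 7-day mean duration, with rank of Day 1, country/region and joint erosion status.
- State in the SAP why the protocol's raw-scale ANCOVA is not used. This is needed even if the Wilcoxon test is kept.
- Keep the Wilcoxon test with its Hodges-Lehmann estimate and interval as a sensitivity or descriptive analysis, noting that this interval need not agree with the adjusted p-value.
- Do not apply to this covariate the rule in SAP 6.13.1.1 that, when Day 1 is missing, "the first available postbaseline score will be used to impute the Day 1 score". It would put a post-treatment value into the adjustment; the SAP itself sets such values aside for the change-from-Day-1 analysis. Use a treatment-blind value such as the overall Day 1 median. With 10% of Day 1 values missing and filled this way (effect 0.30), power was 79.2% against 69.6% for the Wilcoxon test at correlation 0.5, and 89.5% against 69.8% at 0.7. Null rejection was 5.1% for both.

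The cost is SAP wording and minor programming, with no new data. The one drawback is that the adjusted test gives no direct estimate in minutes, which is why the Hodges-Lehmann summary should stay.

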Treatment comparisons of continuous efficacy and health outcomes variables will be made using analysis of covariance (ANCOVA) with country, treatment group, baseline joint erosion status, and baseline value in the model. Type III sums of squares for the least-squares (LS) means will be used for the statistical comparison; the 95% CI will also be reported.

When a restricted maximum likelihood (REML)-based mixed model for repeated measures (MMRM) is used (as a sensitivity model for continuous secondary variables [see Section 6.11.2]), the model will include treatment, country, baseline joint erosion status (1-2 joint erosions plus seropositivity versus at least 3 joint erosions), visit, and treatment-by-visit-interaction as fixed categorical effects and baseline score and baseline score-by-visit-interaction as fixed continuous effects to estimate change from baseline across post-baseline visits. An unstructured covariance structure will be used to model the between- and within-patient errors. If this analysis fails to converge, other structures will be tested such as heterogeneous autoregressive [ARH(1)], heterogeneous compound symmetry (CSH), or heterogeneous Toeplitz (TOEPH). The variance-covariance structure that results in the smallest Akaike information criterion (AIC) will be used. The Kenward-Roger method will be used to estimate the denominator degrees of freedom. Type III sums of squares for the LS means will be used for the statistical comparison; the 95% CI will also be reported. Treatment group comparisons at Week 12 and all other visits will be tested.

The Fisher exact test will be used to perform treatment comparisons for AEs, discontinuations, and other categorical safety data among treatment groups. Change from baseline in continuous vital signs, physical characteristics, and other continuous safety variables, including laboratory variables, will be analyzed using an ANCOVA model with explanatory terms for treatment and the baseline value as a covariate. Type III sums of squares will be used. The significance of within-treatment group changes from baseline will be evaluated by testing whether the treatment group LS mean changes from baseline are different from zero using a t-statistic; the standard error for the LS mean change will also be displayed. Differences in LS means as compared to placebo will be displayed with the associated p-value and a 95% CI of the LS mean difference.

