6.2. Adjustments for Covariates

The covariates used in the parametric statistical model (ANCOVA) of continuous data generally will include the parameter value at baseline. Inclusion of baseline in the ANCOVA model provides estimated adjusted (least squares) means for each treatment reflecting averages for the average baseline patient. Other independent variables that will be included in the models for efficacy and health outcomes analyses to adjust estimates of treatment effect include the stratifying variables country and joint erosion status. When the patient number in each country is deemed small (ie, $n < 30$), countries will be combined into regions (ie, East Asia and Central America). The independent variables used in the logistic regression models will include country/region and joint erosion status (refer to Section 6.1). The stratification variables used in the analyses will be derived based on electronic case report form (eCRF) data and x-ray data collected by Bioclinica.

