The primary analysis of “Worst joint pain” will be analyzed in a similar manner as described for severity of morning joint stiffness NRS. This primary analysis of “Worst joint pain” will be conducted using the mITT population. The PP population results will be used as supportive evidence to the mITT results

- **Recurrence of joint stiffness during the day**

Recurrence of joint stiffness throughout the day is a patient-administered single-item question assessed each day (using a paper diary) through Visit 7 (Week 12) that asks “Did you have any joint stiffness throughout today, other than when you woke up?” (Yes/No).

Recurrence of stiffness during the day will be summarized as a percentage of days with the event at weekly intervals (as defined in Section 6.13.1.1) up to Visit 7 (Week 12).

Percentage of days will be analyzed by week using analysis of variance (ANOVA) with country/region, treatment group, and joint erosion status value in the model. Missing data imputation will follow what was described for the supportive analysis in Section 6.13.1.1.

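### Recurrence of joint stiffness is modelled without the Day 1 diary value already collected, which gives up some precision on an outcome that is not a listed objective

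*SAP*

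**What the plan says.** SAP 6.13.1.2 reduces the daily Yes/No recurrence question to a weekly percentage of days and gives this model: "Percentage of days will be analyzed by week using analysis of variance (ANOVA) with country/region, treatment group, and joint erosion status value". Neither a baseline value nor Day 1 appears.

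SAP 6.13.1.1 shows that a Day 1 answer will exist. Its list of daily diary items ends with "recurrence of morning joint stiffness during the day) will be assessed daily from Week 0 (Visit 2) to Week 12 (Visit 7"), and the analysis weeks are set out as "The weeks are defined as follows: Day 1 on diary, Days 2-8 (Week 1), Days 9-15 (Week 2") and so on to Week 12. Day 1 therefore stands apart from every outcome week.

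The comparable diary measures are treated differently. Stiffness severity is analysed by ANCOVA with treatment, country/region and joint erosion status "as fixed effects and Day 1 value as a covariate". Worst tiredness and worst joint pain follow the same method.

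The general text points the same way. SAP 6.1 plans comparisons of continuous efficacy and health outcomes "using analysis of covariance (ANCOVA) with country, treatment group, baseline joint erosion status, and baseline value in the model". SAP 6.2 says covariates in such models "generally will include the parameter value at baseline". Protocol 12.2.7 treats Day 1 on the diaries as the baseline score for the diary endpoints. The SAP gives no reason for leaving it out for recurrence.

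**The concern.** Differences between patients that a Day 1 answer could explain stay in the residual error of each weekly comparison. If that answer is related to later recurrence, the weekly confidence intervals are wider than they need be, although the data to narrow them have already been collected. No error rate, sample size or primary conclusion is at stake.

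**Working it through.** **The plan's own figure.** The only power statement is 99% for ACR20 (SAP 5.2: 144 per arm, 60% versus 35%, 2-sided 0.05). The pooled rate is 0.475. The null standard error is √(2 × 0.475 × 0.525 / 144) = 0.0589, and the alternative standard error is √((0.60 × 0.40 + 0.35 × 0.65) / 144) = 0.0570. Power = Φ((0.25 − 1.96 × 0.0589) / 0.0570) = 99.1%. The figure reproduces and is untouched by this point. No power, standard deviation or effect size is given for recurrence.

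**Formula.** Let r be the within-arm correlation between the Day 1 value and the weekly percentage of days. Ignoring the one degree of freedom spent (negligible with 288 patients):

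- residual variance ratio, adjusted to unadjusted = 1 − r²
- proportional fall in standard error = 1 − √(1 − r²)
- number of patients the unadjusted model would need for equal precision = 288 / (1 − r²)

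**Inputs.** The 288 comes from SAP 5.2. The value of r is an assumption. The range 0.17 to 0.54 comes from simulated daily Yes/No data with patient random effects (SD 1.5 to 3.5, correlation 0.4 to 0.8 between Day 1 and Week 12).

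| Assumed r | 1 − r² | Fall in SE | Equivalent N |
|---|---|---|---|
| 0.17 | 0.971 | 1.5% | 297 |
| 0.30 | 0.910 | 4.6% | 316 |
| 0.40 | 0.840 | 8.3% | 343 |
| 0.54 | 0.708 | 15.8% | 407 |

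**Check with a binary covariate.** A second simulation used 288 patients, a seven-day percentage outcome, 60% versus 40% of days with recurrence, and a Day 1 Yes/No covariate. The Day 1 Yes rate and the latent correlation between Day 1 and the outcome week were varied. All settings are assumptions.

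| Yes on Day 1 | Latent correlation | r | Simulated fall in SE |
|---|---|---|---|
| 70% | 0.9 | 0.53 | 13.4% |
| 70% | 0.5 | 0.28 | 4.4% |
| 90% | 0.9 | 0.36 | 5.5% |
| 90% | 0.5 | 0.21 | 2.2% |
| 95% | 0.9 | 0.27 | 3.9% |
| 95% | 0.5 | 0.17 | 0.9% |

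The simulated falls broadly follow the formula. At a given latent correlation, the gain shrinks as the Day 1 answer approaches a universal Yes.

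**Missing Day 1.** For the other diary measures, SAP 6.13.1.1 fills a missing Day 1 from the first available postbaseline score. That score dates from Day 2 or later, so it is on treatment, and it can fall within Days 2 to 8, which is the Week 1 outcome. The SAP itself keeps these imputed values out of the change-from-Day-1 analysis. Recurrence currently follows the supportive-analysis rule, which drops weeks with four or more missing scores and needs no Day 1 imputation. Adding a covariate therefore requires a new rule.

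**The case against.** **The baseline is not like for like.** The outcome is a weekly percentage, while Day 1 is one Yes/No answer. SAP 6.2 is qualified by the word generally, and SAP 6.16 also uses ANOVA for the hybrid ACR response, which has no baseline value of its own. This stands in part. A reader might infer that the SAP breaks a binding rule of its own, but the wording does not support that: the omission is an unexplained exception. Nor is recurrence the only diary measure without a Day 1 covariate. Stiffness duration uses a rank-sum test, although SAP 6.13.1.2 adds a change-from-Day-1 analysis for it.

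**Day 1 is not clean.** Protocol 10.2 has the paper diary completed at the end of the day, and SAP 5.3.2 has the Visit 2 dose taken in clinic. Part of a Day 1 recurrence answer therefore covers hours after dosing. Morning-stiffness severity refers to waking, before that dose. One might call it strictly pre-dose, but it is recalled and recorded that evening, so the label is too strong. The SAP already accepts this timing for tiredness and pain, so it is a limitation but does not rule the adjustment out.

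**The gain may be trivial.** Enrolment requires at least 6 tender and 6 swollen joints and hsCRP of at least 6 mg/L (Protocol 8.2.1), so nearly all patients could answer Yes on Day 1. The documents do not show such a ceiling, but it is plausible and would put the gain at the low end.

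**Little depends on it.** Recurrence is a listed health outcome measure (Protocol 10.2) but appears in none of the primary, secondary or exploratory objectives. This stands in full.

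**Conclusion.** The point holds as a minor matter of efficiency. The weekly ANOVA leaves out a Day 1 value that is already collected and that the SAP uses for the three numeric-rating diary measures. On assumed correlations of 0.17 to 0.54, adjustment would shrink the standard error by about 1.5% to 16%. The documents supply no correlation, so neither end of the range can be confirmed.

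Two stronger readings should be resisted. One is that the analysis is biased or invalid: under randomisation the ANOVA estimate is unbiased, and the model already contains both stratification factors. The other is that the omission costs the equivalent of roughly 40% more patients: that is only the top of the assumed range (407 / 288 = 1.41).

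**What to change.** Before unblinding, which SAP 7 places after the final database lock, replace the ANOVA in SAP 6.13.1.2 with a weekly model containing treatment, country/region, joint erosion status and one Day 1 diary value. Choose either Day 1 recurrence (Yes/No) or Day 1 morning-stiffness severity, and name the choice in advance.

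State a treatment-blind rule for a missing Day 1 value, such as the Day 1 mean pooled over both arms or a missing category. Do not carry over the SAP 6.13.1.1 rule that fills Day 1 from postbaseline scores. If the sponsor prefers to keep the ANOVA, one sentence giving the reason would be enough.

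The cost is one extra model term, one missing-data rule, and acceptance of a covariate recorded after the first dose. No new data are needed.
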